13.4.3 Study Summary

The Investigator will submit to the Sponsor on a regular basis copies of the Study Visit Log, which lists all enrolled subjects by Subject Number, initials, and dates of completed visits. The Investigator will submit a final progress report to his/her reviewing IRB within

3 months of study completion at the site. The Investigator will also provide additional reports to the IRB or to the Sponsor upon request.

13.4.4 Retention of Documentation

Essential documents are any records that demonstrate the compliance of the subject, Investigator, Sponsor, and Monitor with the study protocol, ICH-GCP Guidelines, and with all applicable regulatory requirements. Essential documents (including but not limited to study-related correspondence, subject records, subject privacy documentation, records of the distribution and use of all investigational devices, source document worksheets and hardcopies of eCRFs) should be retained and available for audit by the Sponsor's auditor and regulatory authorities until at least 2 years after completion or termination of the study. Suneva requires that it be notified in writing if the Investigator chooses to store the records at a different physical address than the site address or if the Investigator wishes to relinquish ownership of the data so that mutually agreed-upon arrangements can be made for transfer of ownership to a suitably qualified, responsible person.

13.5 Monitoring by the Sponsor

Clinical research staff (monitors) designated by the Sponsor may visit the study center periodically to monitor adherence to the protocol and to applicable FDA regulations, and the maintenance of adequate and accurate clinical records. Monitoring functions will be performed in compliance with ICH-GCP Guidelines. The Investigator agrees to allow these personnel access to the clinical supplies, the Bellafill dispensing and storage area, subject medical records, laboratory data, and other source documentation of the study subjects.

13.6 On-Site Audits

The FDA, in the form of a trained and properly-authorized employee of the department, may request access to all study records, including source documents, for inspection and copying, in keeping with FDA regulations. The Investigator should immediately notify the Sponsor of an upcoming inspection. An auditing inspection may also be conducted by a representative of the Sponsor's Quality Assurance department.

13.7 Proprietary Information

The information generated during this study is considered to be the property of the Sponsor and cannot be used in publication without the written consent of the Sponsor.

13.8 Publications

Suneva, as the Sponsor, has a proprietary interest in this study. Authorship and manuscript composition will reflect joint cooperation among multiple Investigators and sites and Sponsor personnel. Authorship will be established prior to the writing of the manuscript. As this study involves multiple centers, no individual publications will be allowed prior to completion of the final report of the multi-center study except as agreed with the Sponsor.

Appendix 1: Study Assessments

Appendix 2: Microneedling Procedure

Appendix 3: Skin Test Instructions for Use

Appendix 4: Bellafill Instructions for Use

APPENDIX 1: Study Assessments

A. Acne Scar Assessment Scale (ASAS): The ASAS is a static assessment scale that allows the Investigator to measure his/her impression of acne scar severity within the treatment area. The treatment area on each side of the face will be assessed separately, then will be averaged to obtain a global score.

Term	Grade	Description
Clear	1	No depressions are seen in the treatment area. Macular discoloration may be seen.
Very Mild	2	A single depression is easily noticeable with direct lighting (deep). Most or all of the depressions seen are only readily apparent with tangential lighting (shallow).
Mild	3	A few to several, but less than half of all the depressions are easily noticeable with direct lighting (deep). Most of the depressions seen are only readily apparent with tangential lighting (shallow).
Moderate	4	More than half of the depressions are apparent with direct lighting (deep).
Severe	5	All or almost all the lesions can be seen with direct lighting (deep).

B. Physician Global Aesthetic Improvement Scale (PGAIS): The Investigator will refer to baseline photographs and assess global overall improvement (but without considering untreated scars) as per the following:

Rating	Description
5 = Much improved	Marked improvement in appearance from the initial condition, touch-up treatment(s) is not indicted
4 = Improved	Obvious improvement in appearance from the initial condition, but a touch-up or re-treatment is indicated
3 = No change	The appearance is essentially the same as the original condition
2 = Worse	The appearance is worse than the original condition
1 = Much Worse	The appearance is much worse than the original condition

C. Subject Global Aesthetic Improvement Scale (SGAIS): The degree of aesthetic improvement will be assessed by the subject using the SGAIS as defined below. The subject will refer to baseline photographs and assess global overall improvement (but without considering untreated scars) as per the following:

Rating	Description
5 = Much improved	Marked improvement in appearance from the initial condition
4 = Improved	Obvious improvement in appearance from the initial condition
3 = No change	The appearance is essentially the same as the original condition
2 = Worse	The appearance is worse than the original condition
1 = Much Worse	The appearance is much worse than the original condition

D. Quality of Life Scar Impact Scale: The following Quality of Life Scar Impact Scale questionnaire allows the subject to specifically address how acne scarring has affected his/her emotional and functional status:

Please circle the number that best describes how you feel. Circling the number one suggests that you believe that the description on the left hand column best describes how you feel. Circling the number 7 suggests that you believe that the description on the right hand column best describes how you feel. Circling number 4 suggests that you feel neutral or that there has been no change. Please be honest.

The amount and appearance of my acne scarring causes me to feel . . .

1. Less anxious 1 2 3 4 5 6 7 More anxious 2. More optimistic 1 2 3 4 5 6 7 Less Optimistic 3. More energetic 1 2 3 4 5 6 7 Less energetic 4. Eating more healthy food 1 2 3 4 5 6 7 Eating less healthy food 5. Happier 1 2 3 4 5 6 7 Sadder 6. Exercising more 1 2 3 4 5 6 7 Exercising less 7. Less irritable 1 2 3 4 5 6 7 More irritable 8. More amorous 1 2 3 4 5 6 7 Less amorous 9. More social 1 2 3 4 5 6 7 Less social 10. More productive 1 2 3 4 5 6 7 Less productive 11. More focused 1 2 3 4 5 6 7 Less focused 12. Less tired 1 2 3 4 5 6 7 More tired 13. Less angry 1 2 3 4 5 6 7 More angry 14. More confident 1 2 3 4 5 6 7 Less confident 15. More sexually confident 1 2 3 4 5 6 7 Less sexually confident 16. More assertive 1 2 3 4 5 6 7 Less assertive 17. Less argumentative 1 2 3 4 5 6 7 More argumentative 18. More comfortable with others 1 2 3 4 5 6 7 Less comfortable with others 19. More likely to go out 1 2 3 4 5 6 7 Less likely to go out 20. More involved in community activities 1 2 3 4 5 6 7 Less involved in community activities 21. Doing better at work/school 1 2 3 4 5 6 7 Doing worse at work/school 22. More in control 1 2 3 4 5 6 7 Less in control 23. Taking more medications 1 2 3 4 5 6 7 Taking less medications 24. Less depressed 1 2 3 4 5 6 7 More depressed 25. Seen by others as less stressed 1 2 3 4 5 6 7 Seen by others as more stressed 26. Feeling more attractive 1 2 3 4 5 6 7 Feeling less attractive 27. More relaxed 1 2 3 4 5 6 7 Less relaxed 28. Happier when looking in mirror 1 2 3 4 5 6 7 Less happy looking in mirror 29. Using less cosmetics to hide scars 1 2 3 4 5 6 7 Using more cosmetic to hide scars 30. Happier when my face is touched 1 2 3 4 5 6 7 Less happy when my face is touched 1 2 3 4 5 6 7 My life is worse 31. My life is better

Drinking less alcohol

Less happy with my body

32. Drinking more alcohol 1 2 3 4 5 6 7

33. Happier with my body 1 2 3 4 5 6 7

[figure not shown]

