10.2.2 Visit 1: Treatment Visit (D0)

The following activities will be conducted:

- Inclusion/Exclusion Criteria (confirmation)
- UPT (if applicable)
- Review skin test results and inclusion/exclusion criteria to confirm eligibility
- QoL Scar Impact Scale
 - Performed by the subject prior to receiving microneedling treatment.
- Microneedling treatment (see Section 5.1)
- Concomitant Medication/Procedures and AE assessment
- Provide HSV Prophylaxis with Acyclovir for subjects with a medical history of cold sores (may be provided prior to Visit 1 at the discretion of the Investigator).

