10.4 Study Period II (Track B – No Treatment)

10.4.1 Visit 5b (M3 ± 1W)

The following activities will be conducted 24W from Visit 1:

- Concomitant Medication/Procedures and AE assessment
- Facial Scar Photography
- ASAS and PGAIS
 - The Investigator will refer to Baseline photographs for PGAIS evaluation.
- QoL Scar Impact Scale and SGAIS
 - The subject will refer to Baseline photographs for SGAIS evaluation.
- Study Exit

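### QoL Scar Impact Scale: answer 4 can mean neutral or no change, so change from Visit 1 to exit cannot be read reliably

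*Combined protocol and SAP*

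**What the plan says.** Appendix 1 D sets 33 seven-point items under the stem "The amount and appearance of my acne scarring causes me to feel". The two ends are defined as states: "Circling the number one suggests that you believe that the description on the left hand column best describes how you feel" and "Circling the number 7 suggests that you believe that the description on the right hand column best describes how you feel". The midpoint is defined differently: "Circling number 4 suggests that you feel neutral or that there has been no change". No recall period is given, and no time point against which change would be judged.

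The item anchors are comparative words without a comparator, for example "Less anxious 1 2 3 4 5 6 7 More anxious". On 31 items the high end is the unfavourable one. Item 23 ("Taking more medications 1 2 3 4 5 6 7 Taking less medications") and item 32, on alcohol, appear to run the other way.

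The schedule in Section 10.1 places the scale at Visit 1 and at exit only. Section 10.2.2 says of Visit 1: "Performed by the subject prior to receiving microneedling treatment". At exit it is given at Visit 7a for Track A (Section 10.3.3) and at Visit 5b for Track B, where Section 10.4.1 lists "QoL Scar Impact Scale and SGAIS" together. Only the SGAIS is tied to Baseline photographs.

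Section 8 says that subjects will be trained in the self-assessments but does not describe the content. Section 12.2 says that questionnaire data will be reported and allows exploratory tests at 0.05. It gives no QoL total score, scoring direction or rule for change.

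**The concern.** One response code carries both a state and a transition. Giving the scale once before treatment and once at exit makes sense only if it measures a state twice and the two answers are compared. Under that use, an unchanged subject should repeat the Visit 1 answer. The instruction offers another correct answer: at exit, someone who feels exactly as before may circle 4 because nothing has changed. The data then show movement where there was none.

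This cannot be repaired after collection. A 4 that means neutral and a 4 that means no change are the same record, and no other item tells them apart. Even a plain frequency table of exit answers mixes the two. The QoL scale is one of four listed effectiveness measures, so its before-and-after picture is part of what this pilot is meant to deliver.

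**Working it through.** The plan gives no figure for this scale, so there is none to reproduce. The check holds the subject's feelings constant and asks what is recorded.

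**Inputs.** The answer range 1 to 7, the meanings of 1, 4 and 7, and the item directions come from Appendix 1 D. The two time points come from Sections 10.1, 10.2.2, 10.3.3 and 10.4.1. The share *f* of subjects who use the no-change meaning at exit is not in the documents and is an assumption below.

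**Step 1: one item, no true change.** Let *b* be the Visit 1 answer, given as a state. At exit the subject circles 4 for no change. Recorded change = 4 − *b*; true change = 0.

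| *b* | Recorded change | 31 items, high = worse | Items 23 and 32 |
|---|---|---|---|
| 7 | −3 | false gain of 3 | false worsening of 3 |
| 6 | −2 | false gain of 2 | false worsening of 2 |
| 5 | −1 | false gain of 1 | false worsening of 1 |
| 4 | 0 | no error | no error |
| 3 | +1 | false worsening of 1 | false gain of 1 |
| 2 | +2 | false worsening of 2 | false gain of 2 |
| 1 | +3 | false worsening of 3 | false gain of 3 |

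If 4 had one meaning at both visits, the unchanged subject would repeat *b*, and the recorded change would be *b* − *b* = 0 throughout.

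**Step 2: group mean, illustration only.** Mean false shift per item = *f* × (4 − *b*). With everyone at *b* = 6 on a high-is-worse item:

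- *f* = 10%: 0.10 × (−2) = −0.2
- *f* = 25%: 0.25 × (−2) = −0.5
- *f* = 50%: 0.50 × (−2) = −1.0

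With everyone at *b* = 2 the same shares give +0.2, +0.5 and +1.0. The sign and size therefore depend on baseline answers and on *f*, and the documents give neither.

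**Step 3: does the error fall mainly on subjects who do not benefit?** Take two subjects who start at 6 and both answer the exit form in terms of change.

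- Unchanged: circles 4. Recorded gain 6 − 4 = 2, true gain 0, error 2.
- Truly improved from 6 to 5: circles 3 or 2 (assumed) to say that things are better. Recorded gain 3 or 4, true gain 6 − 5 = 1, error 2 or 3.

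The improver can be inflated as much as the unchanged subject, or more.

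**The case against.** The best defence is that the form can be read consistently as a state measure. The stem asks what the scarring causes the subject to feel. In that frame, no change can mean that scarring makes the subject neither more nor less anxious, which is the same as neutral and can be answered at Visit 1. That reading is plausible, but nothing in the text compels it. The comparative anchors and the missing time frame leave the other reading open, and at exit, after months of treatment and follow-up, it is an easy one to adopt.

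The training in Section 8 may help, but its content is not given and the printed instruction still says both things. The SGAIS gives an explicit change rating with a photographic reference, but it covers appearance, not quality of life. It is also true that Section 12.2 never states a comparison of exit with Visit 1. The schedule implies one, and the ambiguity of an exit answer of 4 remains without it.

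The defence does succeed against some wider conclusions. A reader might infer that the wording simply makes unchanged subjects look improved. That holds only for starting answers on the unfavourable side of 4; the rest show false worsening or no error. A reader might also infer that the error gathers in Track B and so shrinks the contrast between tracks. Step 3 shows why this does not follow. Both tracks use the same form, so a between-track bias needs the tracks to differ in how 4 is read, in starting answers or in the size of the error. The open-label design and different exit times make a difference possible, but the documents do not show its direction.

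**Conclusion.** The concern holds in this form: the dual meaning of answer 4 makes within-group QoL change from Visit 1 to exit unreliable. For an unchanged subject who uses the no-change meaning, the error is up to 3 points per item in either direction, and it is zero only if the starting answer was 4. This per-item result follows from the form, given that exit answers are set against Visit 1 answers. Any group-level figure, including the illustration above, rests on assumed baseline answers and an assumed share of subjects, and should not be quoted as an expected bias.

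The effect on Track A versus Track B is of unknown direction. Because the study is a pilot, its inference is exploratory and the QoL scale is one of four effectiveness measures, this is a worthwhile low-cost improvement. It does not put the trial's conclusions as a whole at risk.

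**What to change.** Before the form is first used, change the instruction in Appendix 1 D so that 4 has one meaning, for example: *Circling 4 means that your acne scarring makes no difference to this today.* Add: *Answer for how you feel today; do not compare with an earlier visit.* Use identical text at Visit 1 and at exit, and include the point in the subject training under Section 8.

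The cost is a small form change needing sponsor and IRB approval (Section 13.2), and loss of word-for-word comparability with any earlier use of the form. The protocol calls the ASAS validated but makes no such claim for this scale, so no stated validation is lost. The change does not cure everything: the less/more anchors still lack a comparator, and the apparent reversal of items 23 and 32 needs its own scoring rule.

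If the wording cannot be altered, instruct subjects at both visits to answer for how they feel now, and report QoL change as exploratory with this limitation stated.

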APPENDIX 2: Microneedling Procedure

Pre-skin Treatment

- Exfoliate the skin with a microderm abrasion brush.
- Wash and rinse the skin, pat dry.
- Sterilize the microneedling device per the manufacturer's recommendations.
- Provide anesthesia to the skin surface using a topical anesthetic for up to 30 minutes and/or topical ice pack.
- Remove anesthetic and swab skin with alcohol.

Rolling Technique

- Apply a layer of Regenica Repair Complex to the treatment area before applying the needling device. This will help the needles glide smoothly over the surface of the skin and prevent additional trauma.
- To achieve a uniform distributed prick density, the best recommended approach
 is to begin rolling in a horizontal direction, and after every roll with medium
 pressure, lift the roller and position it a few millimeters from the previous starting
 point, repeating the rolling movement until the entire skin area has been treated.
- When the treatment is complete, apply another layer of Regenica Repair Complex to the region and repeat the process similarly in a vertical direction.
- When rolling, stretch the skin by pulling it with the opposite hand to facilitate needle penetration.
- Most important is to *lift the roller* after each rolling motion, rather than rolling back and forth, to prevent a high skin prick density along the same area. Please see the diagram below:

- Perform rolling on the cheeks, and avoid the orbit and lips.
- Rolling diagonally or back-and-forth produce undesirable effects.
- Rolling diagonally is not recommended. This is not the optimal technique because the center of the diagonal pattern gets a much greater skin prick density than the periphery. A perfectly uniform prick density can only be achieved when rolling at straight angles, such as in a horizontal or vertical direction.

Rolling back-and-forth without lifting the roller is also not recommended due to
extreme prick density distributed over narrow "bands". If the roller is not lifted
after each rolling movement, the roller will resist sideway movements because of
the needles in the skin, producing a "railway effect" as a train on a track. Moving
back and forth produces the same skin pricks, causing a high prick density or
larger-diameter of pricks in the skin.

Post-rolling Treatment

- Erythema typically resolves in 12 hours.
- Place an ice pack if needed for pain.
- Moisturize the skin with Vitamin A & C, and/or Aloe Vera afterwards. Moisturize with a non-irritating moisturizer.
- Apply sunscreen daily, and only after 24hrs post-microneedling treatment

After-use Disinfection of the Microneedle Instrument

 Sterilize the microneedling device per the manufacturer's recommendations; use an appropriate detergent since alcohols do not dissolve proteins as found in blood and skin

APPENDIX 3: Skin Test Instructions for Use

bellafill SKIN TEST INSTRUCTIONS FOR USE

DESCRIPTION

Bellafill® Skin Test is an aseptically produced device composed of purified collagen gel. Each Bellafill® Skin Test consists of 3.5% bovine collagen, 2.7% phosphate buffer, 0.9% sodium chloride, 0.3% lidocaine hydrochloride, and 92.6% water for injection.

INDICATIONS

Bellafill® Skin Test is intended to be administered intradermally into the volar forearm to identify individuals who might show hypersensitivity to injectable bovine dermal collagen devices. Patients so identified are ineligible for treatment with Bellafill®.

CONTRAINDICATIONS

- Bellafill® Skin Test contains bovine collagen and is contraindicated for patients with a history of allergies to any bovine collagen products, including but not limited to collagen injectables (except to verify questionable allergy), collagen implants, hemostatic sponges, and collagen-based sutures, because these patients are likely to have hypersensitivity to the Bellafill® Skin Test.
- Bellafill® Skin Test is contraindicated for patients with severe allergies manifested by a history of anaphylaxis or history or presence of multiple severe allergies.

- Bellafill® Skin Test contains lidocaine and is contraindicated for patients with known hypersensitivity to lidocaine.
- Bellafill® Skin Test is contraindicated for patients undergoing or planning to undergo desensitization injections to meat products, as these injections can contain bovine collagen.

WARNINGS

- If the Skin Test response is positive, the patient must not be treated with Bellafill®. If the Skin Test response is equivocal, it is recommended that a second Skin Test be administered in the opposite arm and evaluated prior to the initiation of treatment.
- Some physicians have reported the occurrence of connectivetissue diseases such as rheumatoid arthritis, systemic lupus erythematosus (SLE), polymyositis (PM), and dermatomyositis (DM) subsequent to collagen injections in patients with no previous history of those disorders. Also, an increased incidence of cellmediated and humoral immunity to various collagens has been found in systemic connectivetissue diseases such as rheumatoid arthritis, juvenile rheumatoid arthritis, and progressive systemic sclerosis (scleroderma). Patients with these diseases may thus have an increased susceptibility to hypersensitivity responses and/ or accelerated clearance of their implants when injected with bovine dermal collagen preparations. Therefore, caution should be used when treating these patients. including consideration for further skin testing.

• Patients with a history of dietary beef allergy should be carefully examined before they are administered the Bellafill® Skin Test since it is possible that the collagen component of the beef may be causing the allergy. More than 1 skin test is highly recommended prior to treating these patients.

PRECAUTIONS

- As with all transcutaneous procedures, Bellafill® Skin Test injection carries a risk of infection.
 The usual precautions associated with injectable materials should be followed.
- Results of the Skin Test may be inaccurate if patients are on immunosuppressive therapy.
- Bellafill® Skin Test should be used with caution in patients who are atopic or have a history of allergies. This class of patient has a greater potential of ultimately exhibiting an allergic reaction to bovine collagen than do other patients.
- Use of Bellafill® Skin Test at specific sites in which an active inflammatory process (skin eruptions such as cysts, pimples, rashes, or hives) or infection is present should be deferred until the underlying process has been controlled.

ADVERSE EVENTS

Rare anaphylactoid responses have been reported with collagen implants, including acute episodes of hypotension, difficulty breathing, tightness in chest, and/or shortness of breath. On rare occasions, the hypersensitivity response has progressed to a cystic reaction which may drain purulent material.

DIRECTIONS FOR USE

Note: The Bellafill® Skin Test should be stored at standard refrigerator temperatures. DO NOT FREEZE.

Prior to being administered the Bellafill® Skin Test, the patient should be provided with a copy of the Bellafill® Skin Test Results Card. The patient should be fully apprised of the purpose of and evaluation criteria for the Skin Test.

- After verifying that contraindications to the proposed Bellafill® treatment do not exist, a Bellafill® Skin Test is administered. At the time of the initial evaluation, a complete medical history should be obtained.
- The Bellafill® Skin Test syringe must be brought to room temperature before injection.
- 3. After cleansing the site, 0.1 cc Bellafill® Skin Test should be implanted intradermally into a volar forearm surface. The results of the Skin Test must be carefully evaluated for a 4-week period prior to the initiation of treatment with Bellafill®. Patients should be instructed to notify their physicians of any untoward test response observed within the 4-week period.
- Discard the syringe after administration of the Bellafill®
 Skin Test.

a. Positive Response

A positive response consists of erythema of any degree, induration, tenderness, and swelling, with or without pruritus, which can appear immediately following implantation and persists for more than 24 hours, or appears more than 24 hours following implantation.

b. Equivocal Response

An equivocal response is one in which there is no localized skin reaction, but the patient does elicit a possible systemic reaction such as a rash, arthralgia (aching joints), or myalgia (aching muscles), which occurs at any time during the 4-week observation period. If

an equivocal response is observed, a second injection in the opposite arm is required, with observation for an additional 4 weeks. Patients demonstrating a positive or equivocal response in this second test should not be treated.

TREATMENT WITH BELLAFILL® IS CONTRAINDICATED IN ANY PATIENT EXHIBITING A POSITIVE RESPONSE OR 2 EQUIVOCAL RESPONSES.

Clinical experience has shown that the importance of screening by means of the Bellafill® Skin Test cannot be overemphasized. However, a negative Skin Test does not preclude the possibility of the

HOW SUPPLIED

Bellafill® Skin Test is an aseptic product packaged in configurations of 2 or 5 syringes in one sealed tray per box. Each syringe contains 0.3 cc of purified collagen gel. Each Bellafill® Skin Test consists of 3.5% bovine collagen, 2.7% phosphate buffer, 0.9% sodium chloride, 0.3% lidocaine hydrochloride, and 92.6% water for injection. Bellafill® Skin Test syringes are appropriate only for testing prior to treatment with Bellafill®.

Each syringe is sealed for singlepatient use. The tip of the syringe is sealed with a tamper-evidence cover. The tray lid is also sealed with a tamper-evidence cover. Do not use if package is damaged or the cover is broken or removed. Do not resterilize.

STORAGE DIRECTIONS

Bellafill® Skin Test syringes should be stored at standard refrigerator temperatures. DO NOT FREEZE.

Bellafill® Skin Test has a clear appearance. In the event that a syringe does not have a clear appearance, do not use the syringe, and notify Suneva Medical at [name] [contact]). Outside the United States, call +[contact].

To place an order, contact Suneva Medical, Inc. In the United States, call toll-free: [name] [contact]).
Outside the United States, call +[contact]. Orders may also be sent by fax to [contact], or email to [contact].

Caution: Federal law restricts this device to physician use only.

SUNEVA MEDICAL, INC.
[name]
United States of America
Toll-Free Phone: [name] [contact])
Outside the U.S. Phone: +[contact]
[contact]
[contact]
www.sunevamedical.com
www.sunevamedical.com

7193 REV01 (10/2014)

